# CCSG catchment Area health pilot – PROMOTE Pilot Study Multimodal communication strategy

The communication training will consist of 5 parts delivered during the session:

- 1) An educational overview of adolescent vaccination, with an emphasis on HPV vaccination
- 2) Overview of the communication strategy
- 3) Process for integrating the communication strategy into clinical workflow at the pharmacy
- 4) Training on communication strategy
- 5) Pharmacy staff practice with the communication strategy

# List of procedures for pharmacy staff

- a. [name], Director of Practice Development for the Washington State Pharmacy Association ( WSPA) will invite independent Western Washington pharmacies to participate in the pilot study
- b. Pharmacy staff at enrolled sites will provide a waiver of written consent to the study team prior to the intervention. Waiver will be provided before completing the pre-implementation survey.
- c. Enrolled pharmacies will ask pharmacy staff to consent to the study and complete the preimplementation survey
- d. Pharmacy staff will complete the 2-part vaccine communication strategy training (2 sessions, 60 minutes each)
  - i. The first session will be online provided as pre-recorded continuing education provided through the Washington State Pharmacy Association (WSPA). This session will be used to teach the vaccine communication strategy.
  - ii. 4-6 weeks later, the second session will be live, in person or conducted online using Zoom, and will also count as CE administered through WSPA. This session will be used to answer any follow-up questions about the training, garner feedback on how the pharmacy staff has been using the vaccine communication strategy, and retrain on any components of the strategy.
- e. The enrolled pharmacies will partake in the communication intervention pilot for up to six months.
- f. After pilot completion, pharmacy staff will be asked to complete the post-implementation survey

# List of procedures to conduct environmental scan of pharmacy (subject to appropriate social distancing procedures)

- a. Study staff will contact the owners of each pharmacy to schedule a time to visit the pharmacies where pharmacy staff who participated in the Aim 2 intervention work.
- b. Under the supervision of the pharmacy managers (in compliance with pharmacy policies and procedures), study staff will be granted permission to enter the pharmacies and conduct the environmental scan.
- c. The study staff member will observe the pharmacy staff and make note of the environment (e.g., workflow set up, features of the pharmacy, medical services provided, etc.) and complete the environmental scan. The scan is designed to avoid disturbing or contacting pharmacy staff while they are working. No personal identification of staff members will be collected during this observation. Study team members completing the environmental scans will be compliant with local jurisdictions' policies and procedures with wearing personal protective equipment (PPE) to reduce risk of coronavirus exposure as needed.

# 6.6 Compensation for study participation

**Participant Incentives.** Compensation of \$50 (as a check, cash, or gift card) will be provided to parents/guardians and pharmacy staff for completing the Aim 1 key informant interviews. Compensation totaling \$40, in the form of cash, will be provided to pharmacy staff for completing the Aim 2 pre- and post-intervention surveys.

**Pharmacy Incentives.** Compensation of \$1,000 (as a check) will be given to each participating pharmacy in the Aim 2 pilot intervention.

#### 6.7 End of study/final contact

Aim 1: Parent/guardian and pharmacy staff participants will exit the study after completing their key informant interview.

Aim 2: Pharmacies will exit the study once their pharmacy staff have completed the post-implementation survey (i.e., post test, 10-15 minutes to complete). This post survey will be administered up to 5 months after the communication strategy intervention has been delivered to the pharmacy sites. The data management team from the participating Western Washington independent pharmacies will conduct an audit of the pharmacy sites' vaccination data and send it to the study team for data analysis using a secure data transfer method approved by the independent pharmacy and Fred Hutch.

# 6.8 Participant retention

For Aim 1, participants who do not present for the key informant interview will be called using contact information obtained at enrollment. A participant will be considered lost to follow up (LTFU) after 5 attempts have been made to contact them on 5 separate occasions without successful rescheduling of an interview. Aim 2's retention is based upon pharmacy contractual agreement to participate in the pilot. Therefore, retention is not applicable.

# 6.9 Participant withdrawal

Participants may voluntarily withdraw from the study for any reason at any time. The PI and research team may also withdraw participants from the study in order to protect their safety.

# 7. Data Management

7.1 Key informant interview audio recordings and transcripts

#### Version 3, 10/27/2022

An interview Excel tracking file with study ID numbers will be used and kept by the project coordinator in a password protected server at Fred Hutch and accessible only to the PI and authorized staff. Participants will be assigned a study ID number to track their interview audio data and transcript.

#### Procedure for audio recordings and transcriptions

- a. One day before the interview, the interviewer will ensure that the recorder is fully operational and that the batteries are charged.
- b. Prior to the start of the interview, the interviewer will test the recorder to ensure that the audio is being well captured.
- c. At the end of the interview, the research staff will play the recording in a private office or room to ensure that the discussion was well captured.
- d. After ensuring the interview was well captured, the interviewer will download the recordings into a Fred Hutch study folder on a secured server.
- e. After the download is done and confirmed, the file in the audio recorder will be deleted.
- f. The interviewer will then hand over the audio recording device to Fred Hutch staff for safekeeping after all the interviews have been completed.
- g. Audio Files will be labeled:

Parent interviews	Parent_ ParticipantNumber_Date Example: Parent_009_2020.05.07
Pharmacy staff interviews	Pharm_ ParticipantNumber_Date Example: Pharm_009_2020.05.07

- a) The audio files will then be uploaded to GMR Transcription to produce a verbatim transcription.
- b) Audio files and transcriptions will be stored on a password protected server at Fred Hutch that only study staff have access to.

# 7.2 Demographic survey

The demographic survey will be completed at the time of the key informant interview is conducted. Once the interview is completed, study staff will ask participants about the demographics (e.g., age, sex/gender, race/ethnicity, etc.) using the questionnaire developed for the survey. The answers will be recorded on a paper survey with the participants' study ID as described in section 7. 1 above. Study staff will enter the data in an electronic database created in either REDCap or Qualtrics. This database will be stored securely on Fred Hutch servers in a password protected folder only accessible by authorized study staff. Paper copies of the demographic survey will be stored in a study folder in either the PI or study coordinator's office at Fred Hutch in a locked file cabinet. Demographic data will also be collected as part of the Aim 2 online surveys mentioned in 7.4 below.

# 7.3 Environmental scan

The environmental scans will be completed by study staff during their observation of the pharmacy under the supervision of the pharmacy owner or their delegate. Study staff will complete the scan using paper copies. The data collected will be entered into an electronic database created in either REDCap or Qualtrics. This database will be stored securely on Fred Hutch servers in a password protected folder only accessible by authorized study staff. Paper copies of the demographic survey will be stored in a study folder in either the PI or study coordinator's office at Fred Hutch in a locked file cabinet.

# 7.4 Pre- and post-implementation survey.

Surveys will be administered online through REDCap or Qualtrics. Participants will be assigned a unique ID to identify their pre- and post-implementation survey responses. These individuals will receive a survey link sent by the study team that will give them secure access to complete the online questionnaire. Survey data will be stored on a password protected server at Fred Hutch. Access to data identifying individual subjects will be restricted to investigators and staff directly involved in the study, all of whom have completed human subjects and standard data confidentiality training.

# CCSG catchment Area health pilot – PROMOTE Pilot Study 7.5 Vaccination audit data from the Independent Pharmacies.

The study team will establish a data use agreement with the independently pharmacies for the secure transfer and management of patient vaccination data from pharmacy sites participating in the pilot intervention. The agreement will describe variables to be included, data format, and data management. Data shall consist of the following for each patient aged 9-17 receiving vaccinations at the pilot sites: Age, sex/gender, race/ethnicity (if captured), insurance status, vaccine type, pharmacy where the patient was immunized, pharmacist who immunized the patient (using a unique code assigned to each pharmacist).

# 7.6 FHCC infrastructure that will secure data files.

The database management is built with multiple layers of security and the center practices appropriate due diligence to ensure the data is maintained in an appropriate manner. The file and database servers at FHCC are housed in a dedicated computer machine room containing emergency backup power, a UPS, a back-up power generator, a non-liquid fire suppression system, and authorization-based limited access. In addition to personal workstations, administrative access to databases and corresponding data will be limited to Virtual Private Network (VPN) and/or Terminal Server access. Furthermore, all databases will reside behind a redundant firewall system and intrusion prevention system.

A copy of the data will be stored in an Amazon Web Services (AWS) VPC. This account is covered by a Business Associates Agreement (BAA) signed by Fred Hutch and Amazon Web Services. The data will be transferred to this secure location via an IPsec VPN tunnel between the Fred Hutch Data Center and the AWS VPC. While stored in the VPC, all data will be encrypted at rest using custom encryption keys managed with AWS Key Management Service. All transport between authorized AWS services including AWS EC2 and AWS S3 will be over secure TLS connections. Any processing of the data will be performed using dedicated EC2 instances to ensure compliance. All access to the AWS Environment is controlled via Security Groups and Network Access Control Lists and audited to ensure no unauthorized access occurs.

The electronic data files for this study will be processed on this dedicated, layered-security system. Access to data identifying individual subjects will be restricted to investigators and staff directly involved in the study, all of whom have completed standard data confidentiality training. Data will be accessed by the study team exclusively using encrypted desktop computers. Per institutional standards, all desktops connecting to Fred Hutch networks must be baselined by Center IT to ensure adequate encryption, password protections, and configuration for the network to recognize an approved device. Unauthorized users do not have access to areas of the network which contain sensitive data, including PHI. All paper records and forms will be stored in locked drawers when not in use. Access to computer records will be strictly controlled and will require simultaneous knowledge of the database structure, database language, and multiple passwords. Since the system is behind a firewall and is accessible only to study staff, the risk of unlawful penetration is not a significant data safeguard concern.

# 7.7 Policies and procedures regarding the physical possession and storage of data files.

Access to data identifying individual subjects will be restricted to investigators and staff directly involved in the study, all of whom have completed standard data confidentiality training. All hard and soft copies of the data with identifiable information will be stored in locked drawers when not in use. Physical media that are received from the distributer or any physical copies of the data will be encrypted while at rest and will be held in a locked cabinet within the user's office. All paper records and forms will be stored in locked drawers when not in use. Secure pulping will be used on any printed material containing individual identifiers

In order to access data, all individuals on the study team must have completed FHCC's Confidentiality Training for Investigators and Research Staff and will have to apply for access according to the Center's Information Security Policy by submitting a CIT Data Services Data Request Form. The granting of access is contingent upon agreement to these security policies, which dictate responsible data usage and the loss of use privileges if violated.

# 7.8 Data destruction

# Study records will be destroyed 7 years after the study IRB file is closed per Fred Hutch data destruction guidelines.

The Aim 2 limited data set from the independent pharmacies, showing vaccination rates, will be destroyed after the study manuscript is published.

Data stored on:	Will be destroyed by:
Server or workstation hard disks, or	Using a "wipe" utility which will overwrite the Data at
Removable media (e.g. floppies, USB flash drives,	least three (3) times using either random or single
portable hard disks) excluding optical discs	character data, or
	Degaussing sufficiently to ensure that the Data
	cannot be reconstructed, or
	Physically destroying the disk
Paper documents with sensitive or Confidential	Recycling through a contracted firm provided the
Information.	contract with the recycler assures that the
	confidentiality of Data will be protected.
Paper documents containing Confidential Information	On-site shredding, pulping, or incineration
requiring special handling (e.g. protected health	
information)	

# 7.9 Endpoints and variables

Aim 1: Qualitative information will be used to evaluate how well the proposed communication strategy matches barriers and facilitators to HPV vaccination in pharmacies for both parents/guardians and pharmacy staff. See interview question guides for the interview content.

Aim 2: Quantitative information will be collected to assess the *acceptability*, *appropriateness*, and *feasibility* of the proposed communication strategy to support HPV vaccination. See the Pre and Post Implementation Survey. Pharmacy audits will be conducted from the pharmacy electronic records to assess *adoption* of HPV vaccination, measured as the average HPV vaccination rate per pharmacist at each pharmacy. We will also assess the impact of the communication strategy on *adoption* of other adolescent vaccines (e.g., tetanus, diphtheria, acellular pertussis; meningoccocal conjugate; influenza).

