Aim 2. This aim will use quantitative approaches to evaluate the feasibility and impact of the communication strategies developed in Aim 1 on adolescent vaccination rates in pharmacies, emphasizing HPV vaccination. We will use a pre/posttest quasi-experimental design to evaluate the change in vaccination rates at selected pharmacy sites after implementation of the multimodal communication strategy, as well as changes in perceptions and behavioral predictors of pharmacy staff. We will also develop an environmental scan to characterize a pharmacy's environment, vaccination workflow, and team dynamics. Conducting environmental scans of pharmacies will further contextualize barriers/facilitators to HPV vaccination.

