# Definition of cases and controls: Not applicable

#### 6.5 Recruitment, screening, consent and enrollment procedures

# 6.5.1 Aim 1

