Description of communication strategy intervention: The communication intervention will be planned to be no more than 120 minutes (target time 90 minutes). The strategy will consist of two evidence-based communication approaches: 1) Electronic forecasting to identify vaccine-eligible children; and 2) Pharmacy staff using the 5A's (Ask, Advice, Assess, Assist, and Arrange) Behavioral Counseling Framework to recommend HPV and other vaccines. Electronic forecasting allows pharmacy staff to proactively check which of their patients are eligible for vaccines. The 5A's Framework is a behavioral counseling approach endorsed by the United States Preventive Services Task and provides an easy rubric for clinicians to evaluate and engage patients' readiness and intentions for behavior change. The two communication approaches would work together by preempting pharmacy staff to proactively engage adolescents/their parents with vaccinations and teach pharmacy staff how to effectively communicate about HPV vaccination. This strategy capitalizes on existing vaccination systems in pharmacies and interpersonal communication training pharmacy staff will be familiar with using with patients.

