# 9. Training procedures and quality assurance

Study PI will supervise training of study staff and clinic/pharmacy staff in study procedures, including recruitment, enrollment, conduct of the interviews, and maintenance of confidentiality and privacy. Specific expertise in the conduct of qualitative research will be provided by our team's qualitative expert, who has conducted qualitative research in numerous settings. All staff have been or will be trained in the responsible conduct of human subjects' research (NIH or CITI courses).

Clinical care: No clinical care will be provided by study staff.

Adherence to protocol: For Aim 1, bi-weekly reporting of enrollment will enable us to monitor if the study is running according to approved protocols. Frequent reporting will also enable us to quickly respond to any problems that may arise during the study.

For Aim 2, we will rely on periodic reporting from the independent pharmacies who will audit their pharmacy records and report their vaccination rates. Periodic reporting will occur at baseline (Month 0) and at least 1 follow-up time point after implementation of the communication strategy (Month 2).

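### Adoption is a rate with no stated denominator, and the listed audit data cannot separate a change in HPV uptake from a change in adolescent traffic

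*Combined protocol and SAP*

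**What the plan says.** Section 7.9 sets the Aim 2 adoption outcome as "measured as the average HPV vaccination rate per pharmacist at each pharmacy". Sections 6.1 and 8.3 use the same definition. None of the three gives a numerator, a denominator or a counting period.

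Section 7.5 describes the audit data: "Data shall consist of the following for each patient aged 9-17 receiving vaccinations at the pilot sites". The variables are "Age, sex/gender, race/ethnicity (if captured), insurance status, vaccine type, pharmacy where the patient was immunized, pharmacist who immunized the patient", the last as a code. Due or eligible status, the number of adolescents served, offers or refusals, and vaccination date are not listed. The same section leaves the variables to be described in a data use agreement.

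On the design, section 6.1 says: "We will use a pre/posttest quasi-experimental design to evaluate the change in vaccination rates at selected pharmacy sites". No comparison pharmacies are planned. Section 9 says of timing: "Periodic reporting will occur at baseline (Month 0) and at least 1 follow-up time point", the latter at Month 2. It relies on the pharmacies, "who will audit their pharmacy records and report their vaccination rates", again without a denominator. Section 7.8 likewise refers to a data set showing rates.

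The strategy itself is aimed at children who are due. Section 6.5.2.B says: "Electronic forecasting allows pharmacy staff to proactively check which of their patients are eligible for vaccines". No section sends that list to the study or uses it in the outcome.

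**The concern.** The strategy is meant to work by finding vaccine-eligible children and prompting staff to engage them. A change in adoption would naturally be read as a change in how often such children are vaccinated. The listed data hold neither the children who left with no vaccine nor any marker of who was due. The number of adolescents coming through the pharmacy is therefore mixed into whatever rate is calculated.

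In a pre/post comparison without control sites, this matters directly. If more adolescents come in during the follow-up window, the outcome can rise with no change in staff behaviour. If fewer come in, a real improvement can disappear. The pilot is meant to indicate potential impact ahead of a larger trial (section 6.4), so a volume artefact could carry forward into that trial's planning.

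**Working it through.** The plan gives no expected rate, effect size or sample-size calculation for Aim 2, so there is no figure to reproduce. The check asks what the listed data can yield and how each quantity behaves. Every count below is an assumption for illustration. The only figure from the documents is the 15% rise in adult vaccinations in an earlier forecasting study at a pharmacy chain (section 4, Rationale).

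**Quantity 1: HPV doses per pharmacist.** With staffing fixed,

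doses per pharmacist = (due children seen per pharmacist) × (uptake among due children).

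Take 40 due children per pharmacist and 10% uptake at baseline: 40 × 0.10 = 4.0.

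Uptake unchanged, traffic changes:
- Traffic +15%: 46 × 0.10 = 4.6, a change of +15%.
- Traffic +30%: 52 × 0.10 = 5.2, a change of +30%.
- Traffic −20%: 32 × 0.10 = 3.2, a change of −20%.

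The percentage change equals the traffic change whatever starting values are used. For example, 40 children at 5% uptake or 100 at 20% also give +15% when traffic rises 15%. Per due child, the rate is 10% in every case above (4.6/46, 5.2/52, 3.2/32).

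Uptake truly up 15% in relative terms, traffic changes:
- Traffic −13%: 1.15 × 0.87 = 1.00, an observed change of about 0%.
- Traffic −20%: 1.15 × 0.80 = 0.92, an observed change of −8%.

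**Quantity 2: HPV share of vaccinated adolescents.** Let H be HPV recipients and O the vaccinated adolescents who received only other vaccines. The share is H/(H + O). It falls exactly when O grows by a larger factor than H.

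- Baseline: 10/(10 + 30) = 25%.
- H to 15 (×1.5), O to 60 (×2): 15/75 = 20%. HPV doses rise by half and the share falls.
- H to 15 (×1.5), O to 40 (×1.33): 15/55 = 27.3%. The share rises.
- H fixed at 5, O from 10 to 20: 5/15 = 33% becomes 5/25 = 20%, with no change in HPV doses.

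The direction is therefore not fixed. Adoption of other adolescent vaccines, including influenza, is also an outcome (sections 6.1 and 7.9), so movement in O is to be expected.

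**Does another provision cover this?** Section 6.5.2.B selects pharmacies with similar case load. That addresses differences between sites, not change within a site over time. Section 8.3 names nonparametric pre/post tests, with no adjustment for volume. Section 13 lists only generalizability as a limitation.

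**The case against.** The strongest reply is that the rate is undefined rather than wrongly defined. The pharmacist may be only the unit over which rates are averaged, not the divisor. The pharmacies report rates themselves, and the data use agreement could still specify a suitable denominator. That stands as far as it goes: the documents do not establish that the measure divides by pharmacists. But section 7.5 states what the data shall consist of, and that list supplies no count of due or served adolescents.

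Three stronger readings are tempting and not supported:
- A reader might infer that every due child who missed HPV vaccine is left out. A due child given only another vaccine is in the extract, though not marked as due. Only children given no vaccine are absent.
- A reader might infer that the HPV share must fall whenever other vaccines increase. It falls only if they grow proportionally more than HPV, and the plan emphasizes HPV.
- A reader might infer that Aim 2 is defined as the proportion of due children vaccinated. The documents speak of impact and of change in vaccination rates at sites. A pharmacist-level adoption measure is a coherent choice and need not be dropped.

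Two further objections shape the remedy. Proactive engagement may itself bring adolescents in, so dividing by those served could hide a genuine gain. And the cited forecasting experience comes from a chain, while Aim 2 uses independent pharmacies; nothing shows that they can reconstruct due status for a baseline window.

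Pilot status excuses the absence of a power calculation, which section 6.4 addresses. It does not settle what the outcome measures, since section 6.1 undertakes to evaluate impact on vaccination rates.

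**Conclusion.** The point holds in this form: no denominator is stated, and the data listed in section 7.5 support only HPV doses per pharmacist or the HPV share of vaccinated adolescents. The first moves one-for-one with adolescent traffic at constant uptake and staffing. The second can move against HPV doses. Without comparison pharmacies, neither separates a strategy effect from a change in volume between audits.

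The size in this study is unknown because the documents give no volumes. As a scale, a 15% traffic change alone would reproduce the only effect size the plan cites, and a 13% fall would cancel a true effect of that size. The dependence on traffic follows from the identity and does not rest on the assumed counts. This should be changed before the audit data are drawn, but it does not undermine the pilot's other aims.

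**What to change.** In section 7.5 and the data use agreement, add:
- the vaccination date for each record;
- one aggregate count per site and audit window of distinct patients aged 9-17 served;
- where the forecasting system can produce it for both windows, the number of these patients due for HPV vaccine.

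State pre and post windows of equal length and apply the same counting rule in both. The windows need stating because follow-up appears as Month 2 (section 9), up to 5 months (6.7) and up to six months (6.5.2.B).

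In sections 7.9 and 8.3, define and report for each pharmacy HPV doses per 100 such patients, alongside HPV doses per pharmacist and the served count itself. Showing all three keeps visible any traffic that the strategy brings in.

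The cost is a small extra data pull and wording changes in three sections and the agreement. Patient lists may contain inactive records, which is why one counting rule must apply to both windows. Due status may be unavailable at baseline; the served count is then the fallback, and it removes volume change only if the fraction of served adolescents who are due stays stable. Time trends other than volume remain without comparison sites and should be added to section 13.

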# CCSG catchment Area health pilot – PROMOTE Pilot Study **8.3 Data analysis**

# For both Aim 1 & Aim 2:

**Aim 1:** Using community-based sampling in collaboration with the Fred Hutch Office of Community Engagement and Outreach, we will conduct audio-recorded, semi-structured interviews with parents of children aged 9-17 (up to *n*=12) and Bartell Drugs pharmacy staff (up to *n*=18; 9 pharmacists, 9 pharmacy technicians) to evaluate how well our proposed communication strategy match barriers and facilitators to HPV vaccination in pharmacies. Interview guides will be informed by the TDF, a widely used theoretical framework to understand behavioral determinants to successfully implement health promotion programs. Interviews will be about 90 minutes and qualitative data will be analyzed using framework-guided rapid analyses described by Gale et al. The qualitative data will be used to adapt the pharmacy staff's workflow to improve their use of the electronic forecasting system and develop a tailored vaccine communication training based on the 5A's. Adaptations made to the communication strategy will be methodically documented using Stirman's *Taxonomy of Adaptation Characteristics*.

**Aim 2:** We will evaluate the impact of the communication strategy using a pre/post implementation study design in independent pharmacies located in Western Washington state. This design is commonly used in exploratory/development studies. The communication strategy will be delivered at the pharmacy study sites by study staff members. We will use the IOF which identifies distinct implementation outcomes widely used to determine how successful implementation of an evidence-based practice, like HPV vaccination, was in a specified setting, like pharmacies. We will use validated survey measures to assess pharmacy staff's report of the *acceptability, appropriateness,* and *feasibility* of the communication strategy to support HPV vaccination. We will also conduct audits of the pharmacy electronic records to assess *adoption* of HPV vaccination, measured as the average HPV vaccination rate per pharmacist at each pharmacy. We will also assess the impact of the communication strategy on *adoption* of other adolescent vaccines using pre-post data analysis methods like Wilcoxon signed-rank test or other nonparametric tests appropriate for small sample statistics.

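### Influenza is named among the vaccines used to judge the strategy's impact, but the uncontrolled Month 0 to Month 2 audit is not anchored to the calendar, so the change can reflect the start month

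*Combined protocol and SAP*

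**What the plan says.** Section 6.1 sets the Aim 2 design: "We will use a pre/posttest quasi-experimental design to evaluate the change in vaccination rates at selected pharmacy sites". Sections 6.1 (Aim 2 outcomes) and 7.9 add a further outcome, the impact of the strategy on adoption "of other adolescent vaccines (e.g., tetanus, diphtheria, acellular pertussis; meningoccocal conjugate; influenza". Section 8.3 gives the analysis, naming no vaccine: adoption "of other adolescent vaccines using pre-post data analysis methods like Wilcoxon signed-rank test" or another small-sample nonparametric test. Adoption is defined only for HPV, "measured as the average HPV vaccination rate per pharmacist at each pharmacy", with no denominator or time window.

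The timing statements are:
- Section 9: "Periodic reporting will occur at baseline (Month 0) and at least 1 follow-up time point after implementation of the communication strategy (Month 2".
- Section 6.5.2.B, procedures for pharmacy staff: "The enrolled pharmacies will partake in the communication intervention pilot for up to six months".
- Section 6.7: "This post survey will be administered up to 5 months after the communication strategy intervention has been delivered to the pharmacy sites". The same section describes the vaccination audit but gives it no date.

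No comparison group is described, and the entry just before section 6.5 reads "Definition of cases and controls: Not applicable". The stated control for confounding is to choose pharmacies with similar case load and community characteristics (section 6.5.2.B). The limitations in section 13 cover only generalizability. The audit variables in section 7.5 include vaccine type, pharmacy and a pharmacist code, but not the date of vaccination.

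**The concern.** A pre-post comparison without controls attributes to the intervention whatever else changed between the two times. For an outcome with a yearly cycle, part of that change is predictable. If influenza doses cluster in some months, two audits two months apart sit at different points of the cycle, and the difference between them has a sign and size fixed by the start month. Choosing similar pharmacies does not help, because they share the same calendar. A shared season moves all sites in the same direction, which is the pattern a signed-rank test picks up.

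What is at stake is the influenza part of a further outcome. Section 6.4 describes the pilot as a way to understand potential impact and looks ahead to a large-scale trial. A calendar-driven influenza change read as a strategy effect would misinform that planning.

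**Working it through.** The plan states no sample size, alpha or effect size for Aim 2, so there is no figure to reproduce. Three checks were made.

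**1. No-effect ratio, Month 2 to Month 0**

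From the documents: audits at Month 0 and Month 2, and no comparison group. Assumed, because the documents are silent: each audit covers one calendar month; the rate moves in proportion to doses; and monthly shares of annual influenza doses from January to December are 8, 6, 5, 4, 4, 4, 5, 8, 14, 18, 14 and 10% (sum 100%). This is the mild curve.

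Formula: ratio = share in month m+2 / share in month m.

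| Month 0 to Month 2 | Ratio with no strategy effect |
|---|---|
| Jan to Mar | 5/8 = 0.63 |
| Feb to Apr | 4/6 = 0.67 |
| Mar to May | 4/5 = 0.80 |
| Apr to Jun | 4/4 = 1.00 |
| May to Jul | 5/4 = 1.25 |
| Jun to Aug | 8/4 = 2.00 |
| Jul to Sep | 14/5 = 2.80 |
| Aug to Oct | 18/8 = 2.25 |
| Sep to Nov | 14/14 = 1.00 |
| Oct to Dec | 10/18 = 0.56 |
| Nov to Jan | 8/14 = 0.57 |
| Dec to Feb | 6/10 = 0.60 |

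The range is 0.56 to 2.8, and two start months give no distortion. A flat curve gives 1.0 throughout. A steeper assumed curve (peak month 32%) gives 0.25 (8/32, October start) to 50 (25/0.5, July start). The 50 comes from a near-zero summer base and should not be taken as an expected size. A baseline from the same calendar month a year earlier gives 1.0 under any of these curves, provided the season does not change from year to year.

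**2. What the signed-rank test can show**

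If all n units move the same way, the smallest two-sided exact p is 2/2^n:
- n = 2 pharmacies: 2/4 = 0.50
- n = 4 pharmacies: 2/16 = 0.125
- n = 6 pharmacists: 2/64 = 0.031

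Section 6.5.2.B plans 2 to 4 pharmacies. Section 6.3.1 allows up to 25 staff, without saying how many are vaccinating pharmacists.

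**3. False positives with pharmacists as units**

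A simulation with no strategy effect used 1,500 runs per setting, Poisson counts, volumes varying between pharmacists, an exact signed-rank test at an assumed two-sided 0.05, and August or November starts. With 8 or 12 pharmacists giving on average 24 or 60 influenza doses a year each (assumed), the mild curve gave 22% to 99% false positives. The flat curve gave 2% to 4%. With the mild curve and a same-month prior-year baseline (November start), the rate was 2.6% to 4.2%.

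**The case against.** The strongest objection is that the plan has not chosen a faulty window, because it has chosen none. Section 9 says when reports are due, under adherence to protocol, and not what period each covers. This stands, and the ratios above therefore depend on the assumed one-month windows. It does not remove the problem, since nothing in the plan steers the audit towards a season-neutral window. If both reports looked back 12 months, season would largely cancel, but two reports two months apart would share 10 of those 12 months and could show little of any strategy effect.

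A reader might infer a much larger distortion by comparing a six-month pilot with the six months just before it. If 70% to 95% of doses fall in the peak half-year, s/(1-s) gives 0.70/0.30 = 2.3 to 0.95/0.05 = 19. The documents do not support that reading. No section states this contrast, six months is a maximum, and the figures need the windows to match the peak and off-peak halves exactly.

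A reader might also infer that a pooled figure for other vaccines would be distorted. No pooled figure is planned, and vaccine type is collected, so vaccine-specific results are possible.

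It is also fair that influenza is one example within a further outcome, that HPV is the focus, and that this is an unpowered pilot. These points limit the weight of the concern. They do not make the influenza estimate interpretable.

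**Conclusion.** The concern holds for the influenza component of the other-vaccines outcome. As planned, an influenza change from Month 0 to Month 2 cannot be separated from the calendar. Under the mild assumed curve, the apparent effect with no strategy effect lies between roughly a halving and nearly a tripling, depending on the start month.

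This rests on influenza vaccination being seasonal, on one-month audit windows, and on a rate that follows dose counts. The documents quantify none of these. With pharmacies as units, the consequence is a misleading estimate and not a significant p-value, so it would be too strong to say the pilot must report clear success or clear harm. With six or more pharmacists as units, false significance is possible. The plan does not name the unit for this test. No seasonal distortion of the HPV, tetanus-diphtheria-pertussis or meningococcal results has been shown here.

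**What to change.** - **Section 7.5:** add date of vaccination to the audit variables and the data use agreement. Calendar matching depends on it.
- **Sections 7.9, 8.3 and 9:** define the period each audit covers, and reconcile the Month 2 audit with the pilot of up to six months and the survey at up to 5 months.
- **Influenza baseline:** take it from the same calendar months of the prior year in the same pharmacy records, and show the adjacent baseline beside it.
- **Reporting:** give influenza separately from the other adolescent vaccines. Where prior-year data are unavailable or not comparable, describe the influenza doses and draw no conclusion about impact.

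The cost is one added variable, one further retrospective extract from records already being audited, and a few sentences of text. No new sites, participants or visits are needed.

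The downside is that a prior-year baseline carries year-to-year change, and the protocol's coronavirus precautions are a reason to check whether the prior year is comparable. Staff turnover can break the pairing by pharmacist, so the prior-year influenza comparison may have to be made by pharmacy. With at most four sites it would then serve as an estimate and not as a test.
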